9.5.2 Insurance, Indemnity, and Compensation

Aclaris will maintain an appropriate clinical study insurance policy.

9.5.3 Financial Disclosure

Investigators and sub-investigators will provide the sponsor with sufficient, accurate financial information as requested to allow the sponsor to submit complete and accurate financial certification or disclosure statements to the appropriate regulatory authorities.

10 RECORDS MANAGEMENT

All clinical study information should be recorded, handled, and stored in a way that allows its accurate reporting, interpretation, and verification. This principle applies to all records referenced in this protocol, irrespective of the type of media used.

An eCRF will be used to store and transmit patient information. The eCRF must be reviewed and electronically signed and dated by the investigator. The investigator is responsible for verifying that the data entries are accurate and correct by signing the eCRF.

Access to the eCRF will be strictly password protected and limited to personnel directly participating in the study. Data should be entered into the eCRF completely by authorized site personnel (e.g., investigators and the study coordinator). The eCRF must be completed as soon as possible after any patient evaluation or communication. If data are to be changed due to erroneous input or other reason, an electronic audit trail will track these changes. The eCRFs and computers that store them must be accessible to study monitors and other regulatory auditors.

During each study visit, a physician participating in the study will maintain progress notes in the patient's medical records to document all significant observations. At a minimum, these notes are to contain:

- The date of the visit and the corresponding day or visit in the study schedule
- General condition and status remarks by the patient, including any significant medical findings. The severity, frequency, duration, and resolution of any reported AE, and the investigator's assessment as to whether or not the reported AE is related to study medication
- Changes (including dosages) in concomitant medications/therapies (including medical foods) or procedures
- A general reference to the procedures completed
- The signature or initials of all physicians making an entry in the medical record (progress notes)

In addition, any contact with the patient via telephone or other means that provides significant clinical information is to also be documented in the medical record (progress notes), as described above.

Information from the medical records (progress notes) and other source documents is to be promptly entered into the appropriate section of the eCRF.

Changes to information in the medical record (progress notes) and other source documents are to be initialed and dated on the day the change is made by the investigator (or designee). If the reason for the change is not apparent, a brief explanation for the change is to be written adjacent to the change. Changes to the eCRF will be electronically tracked.

10.1 Source Documentation

Source documents contain the results of original observations and activities of a clinical investigation. They are the original records in which raw data are first recorded. Source documents include, but are not limited to, medical records (progress notes), ECG and computer printouts, screening logs, completed scales, quality of life questionnaires, and recorded data from automated instruments.

The investigator/site personnel should maintain adequate and accurate source documents and study records that include all pertinent observations on each of the site's study patients. Source data should be attributable, legible, contemporaneous, original, accurate, and complete. Changes to source data should be traceable, should not obscure the original entry, and should be explained if necessary (e.g., via an audit trail).

All source documents from this study are to be maintained by the investigator and made available for inspection by authorized persons. The investigator will provide direct access to source documents/data for study-related monitoring, audits, IRB/IEC review, and regulatory inspections. The sponsor should verify that each patient has consented, in writing, to direct access to his/her original medical records for study-related monitoring, audit, IRB/IEC review, and regulatory inspection.

10.2 Electronic Case Report Form Completion and Data Management

An eCRF will be used to store and transmit patient information. The file structure and format for the eCRF will be provided by the sponsor or its representative and should be handled in accordance with the instructions provided.

The eCRF must be reviewed and electronically signed and dated by the investigator.

Access to the eCRF will be strictly password protected and limited to personnel directly participating in the study. Data should be entered into the eCRF completely by authorized site personnel (e.g., investigators and the study coordinator). The eCRF must be completed as soon as possible after any patient evaluation or communication. If data are to be changed due to erroneous input or other reason, an electronic audit trail will track the changes. The eCRFs and computers that store them must be accessible to study monitors and other regulatory auditors. Changes to the eCRF will be electronically tracked.

Data will be entered/loaded into a validated electronic database using a clinical data management system. Computerized data cleaning checks will be used in addition to manual review to check for discrepancies and to ensure consistency of the data.

10.3 Study Files and Record Retention

All data derived from the study will remain the property of the sponsor. The sponsor assumes accountability for actions delegated to other individuals.

Page 60 of 71

Records must be retained in accordance with the current ICH Guidelines on GCP. All essential study documents, including records of patients, source documents, eCRFs, and the study medication inventory, must be kept on file.

Essential documents should be retained until at least 2 years after the last approval of a marketing application in an ICH region and until there are no pending or contemplated marketing applications in an ICH region, or until at least 2 years have elapsed since the formal discontinuation of clinical development of ATI-450. However, essential documents may be retained for a longer period if required by the applicable regulatory requirements or by agreement with the sponsor. The sponsor is responsible for informing the investigator when these documents need no longer be retained.

The investigator is not to dispose of any records relevant to this study without written permission from the sponsor and is to provide the sponsor the opportunity to collect such records. The investigator shall take responsibility for maintaining adequate and accurate hard copy source documents of all observations and data generated during this study. Such documentation is subject to inspection by the sponsor, its representatives, and regulatory authorities.

If an investigator moves, withdraws from a study, or retires, the responsibility for maintaining the records may be transferred to another person who will accept responsibility. Notice of transfer must be made to and agreed by the sponsor.

11 AUDITING AND MONITORING

Sponsor-assigned monitors will conduct regular site visits to the investigational facilities for the purpose of monitoring various aspects of the study, such as assessing patient enrollment, compliance with protocol procedures, completeness and accuracy of data entered into the eCRFs, verification of eCRF data against original source documents, and occurrence of AEs. The investigator must agree to sponsor-authorized personnel having direct access to the clinical (or associated) files and clinical study supplies (dispensing and storage areas) to ensure compliance with applicable regulations, and the investigator will assist with the sponsor's monitoring activities.

Quality control will occur at each stage of data handling to ensure that all data are reliable and have been processed correctly. The sponsor should ensure oversight of any study-related duties and functions carried out on its behalf.

The CRFs should be completed in a timely manner and on an ongoing basis to allow regular review by the study monitor.

Details describing the strategy, responsibilities, and requirements of the study monitoring are provided in the study monitoring plan.

The purpose of an audit is to assess whether ethics, regulatory, and quality requirements are being fulfilled. The sponsor or its representative may conduct audits at the investigative sites including, but not limited to, drug supply, presence of required documents, the informed consent process, and comparison of CRFs with source documents. Government regulatory authorities may also inspect the investigator during or after the study. The investigator (or designee) should contact the sponsor/CRO immediately if this occurs. All medical records (progress notes) must be available for audit. The investigator must agree to participate with audits conducted at a convenient time in a reasonable manner.

11.1 Risk and Quality Tolerance Limits

The sponsor will review risk control measures outlined within the study specific monitoring plan periodically to ascertain whether the implemented clinical quality management activities remain effective and relevant. The clinical quality management approach and any important deviations from the predefined quality tolerance limits and remedial actions adopted will be described in the CSR.

11.2 Protocol Adherence and Deviations

The investigator and site personnel should conduct the study in compliance with the protocol and should use continuous vigilance to identify and report protocol deviations.

A protocol deviation is any change, divergence, or departure from the study design or procedures defined in the protocol that may be on the part of the investigator, site personnel, or the patient.

Page 62 of 71

Important protocol deviations are a subset of protocol deviations that may significantly impact the completeness, accuracy, and/or reliability of the study data or that may significantly affect a patient's rights, safety, or well-being. For example, important protocol deviations may include enrolling patients in violation of key eligibility criteria designed to ensure a specific patient population or failing to collect data necessary to interpret primary endpoints, as this may compromise the scientific value of the study.

The investigator should not implement any deviation from the protocol without agreement from the sponsor and prior review and approval from the IRB/IEC of an amendment, except where necessary to eliminate an immediate hazard to a study patient, or when the change involves only logistical or administrative aspects of the study, such as a change in a monitor or telephone number.

In the event of an important protocol deviation, the investigator will discuss the deviation with the sponsor's medical monitor and will come to an agreement as to whether the patient should be withdrawn from the study due to the important protocol deviation.

Page 63 of 71

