4.4.2 Premature Discontinuation from the Study

Participation in the study is strictly voluntary. A patient has the right to withdraw from the study at any time for any reason, without any reprisal.

The investigator has the right to terminate participation of a patient for any of the following reasons:

- Difficulties in obtaining blood samples
- Violation of the protocol
- Any other reason relating to integrity of the study data

If a patient is withdrawn from the study, the study monitor/sponsor will be informed immediately. If there is a medical reason for withdrawal, the patient will remain under the supervision of the investigator until satisfactory health has returned.

If the patient withdraws consent for disclosure of further information, the sponsor may retain and continue to use any collected data before such a withdrawal of consent. If a patient withdraws from the study, he/she may request destruction of any samples taken and not tested, and the investigator must document this in the site study records.

Although a patient is not obliged to give his/her reason(s) for withdrawing prematurely from a study, the investigator should make a reasonable effort to ascertain the reason(s), while fully respecting the patient's rights.

At the time of premature study discontinuation, the investigator should make every effort to ensure the patient completes the assessments indicated at the end of study (Day 84) and safety follow-up visit (Day 7); see Table 1.

Patients who prematurely discontinue from the study cannot subsequently rejoin the study. For details on the discontinuation of study sites or the study as a whole, see Section 14.

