5.2 Efficacy Assessments

5.2.1 Physician Completed Efficacy Questionnaire

The Physician's Global Assessment of Autoinflammatory Disease Activity (PGA) is a measure to be completed by the investigator or designee. The PGA uses a 5-point rating scale: absent, minimal, mild, moderate, and severe. The investigator will select a rating based on the patient's current disease activity at the time of the visit.

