6.2 Blinding

This is an open-label trial.

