6.6 Concomitant Medication

The following medications are prohibited during the duration of the study:

- 1. Systemic immunosuppressant or immunomodulatory therapy (excluding anti-IL-1 therapy for treatment of CAPS during screening and follow-up period). See section 3.1 for washout information.
- 2. JAK inhibitors (systemic and topical).
- 3. Systemic corticosteroids (Intranasal, inhaled, and topical ocular corticosteroids) are allowed.

All medication (including vaccines, over-the-counter or prescription medicines, vitamins, and/or herbal supplements) taken from 30 days before start of screening until the end of the follow-up period will be recorded in the appropriate section of the eCRF. The following details must be recorded in the eCRF:

- Medication name (ideally the generic name)
- Reason for use
- Start and end date of administration
- The dose and frequency of administration

The medical monitor should be contacted if there are any questions regarding prior or concomitant medication or procedures.

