8.2 Analysis Populations

- The ITT population will include all patients who have been administered at least one dose of study medication.
- The PP population will include all patients who complete 12-weeks of treatment and 4-weeks of follow up and have completed assessments.

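### Sections 11.2 and 4.4.2 let a dosed patient be withdrawn from the study for a protocol deviation, without criteria and with the outcome open to view, so later efficacy data can be missing because of relapse

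*Combined protocol and SAP*

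**What the plan says.** Section 11.2 defines important deviations by open-ended examples: enrolment against key eligibility criteria, or "failing to collect data necessary to interpret primary endpoints". After such a deviation the investigator and the sponsor's medical monitor "will come to an agreement as to whether the patient should be withdrawn from the study due to the important protocol deviation". The exit is from the study, not only from ATI-450.

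Section 4.4.2 separately allows the investigator to end a patient's participation. Its grounds include "Violation of the protocol" and "Any other reason relating to integrity of the study data". Patients who leave cannot rejoin.

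Other sections bear on this:
- Section 6.2: "This is an open-label trial". Section 5.2.1 says the PGA "is a measure to be completed by the investigator or designee". Section 9.4 provides no data monitoring committee.
- Section 6.6 opens with "The following medications are prohibited during the duration of the study". It exempts anti-IL-1 therapy only during screening and follow-up.
- Section 8.2 keeps every dosed patient in ITT and restricts PP to "all patients who complete 12-weeks of treatment and 4-weeks of follow up and have completed assessments".
- Section 8.4.5 uses the visits attended, takes the withdrawal visit as the end-of-study assessment, and replaces it with the previous visit if it falls more than 1 day after the last dose. Missing ITT efficacy data go to model-based multiple imputation where appropriate, with the rules deferred to the SAP.

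**The concern.** Deviations in this trial need not be independent of outcome. A patient whose CAPS returns and who resumes anti-IL-1 therapy during the treatment period has departed from Section 6.6. If that is judged important, the relapse itself opens the decision on withdrawal. An eligibility error found after dosing could likewise be tolerated in a patient who is well and acted on in one who is not.

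The decision is made case by case. The investigator's own team rates the PGA, and nothing requires the decision to be taken without sight of disease status. A withdrawn patient's later scheduled visits are then missing for a reason tied to the result. The data at stake are the remission, Key Symptom Score (KSS) and relapse summaries. With up to 10 patients and no control arm, one such decision moves a proportion by several points, and no comparator would reveal it.

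**Working it through.** **The plan's own figure.** There is none to reproduce. Section 8.3 sets enrolment at up to 10 on feasibility and gives no expected remission rate, power or dropout rate. The counts below are assumptions.

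**Step 1: from relapse to missing data.**
- Section 6.6 makes anti-IL-1 therapy during treatment a deviation.
- Section 11.2 then permits withdrawal from the study, and Section 4.4.2 asks for best efforts at the Day 84 and Day 7 assessments. Neither asks for the visits in between.
- Visits fall on Days 14, 28, 56 and 84. A patient who relapses after Day 56 and attends the withdrawal visit more than 1 day after the last dose has the previous visit used as end of study under Section 8.4.5. That visit may show remission.
- Otherwise the gap is open to imputation. The combined document as supplied states no rule that counts a withdrawn patient as a failure.

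**Step 2: size.** Let N = 10 dosed patients, x = 5 truly in remission at Week 12, and k = failing patients lost. The rate among the rest is p = x/(N − k). If the lost patients are imputed like the rest, the expected ITT rate is (x + k·p)/N, which equals p.

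| k | Rate among the rest | Exact (Clopper-Pearson) 95% interval | Expected ITT if imputed like the rest |
|---|---|---|---|
| 0 | 5/10 = 50.0% | 18.7 to 81.3% | 50.0% |
| 1 | 5/9 = 55.6% | 21.2 to 86.3% | (5 + 0.556)/10 = 55.6% |
| 2 | 5/8 = 62.5% | 24.5 to 91.5% | (5 + 1.250)/10 = 62.5% |
| 3 | 5/7 = 71.4% | 29.0 to 96.3% | (5 + 2.143)/10 = 71.4% |

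**Step 3: range over the assumption.** For x from 4 to 7, one loss adds between 4/9 − 4/10 = 4.4 and 7/9 − 7/10 = 7.8 points. Two losses add between 4/8 − 4/10 = 10 and 7/8 − 7/10 = 17.5 points.

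**Step 4: the previous-visit rule.** With x = 5, suppose each lost patient was in remission at the previous visit and was seen more than 1 day after the last dose. End-of-study ITT becomes (5 + k)/10 = 60%, 70% or 80%. This is the unfavourable extreme of that rule, not an expected value.

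**Step 5: after the change.** If all 10 are followed, or patients who start prohibited therapy during treatment are counted as not in remission from then on, the ITT figure in this example returns to 5/10 = 50.0%.

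**The case against.** The strongest reply is that the plan already limits the damage, and much of it stands.

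- **Trigger.** Only important deviations open Section 11.2.
- **Exit data.** Section 4.4.2 seeks the Day 84 and Day 7 assessments at exit. Under Sections 8.2 and 8.4.5 a dosed patient stays in ITT and attended visits are used. A relapse already recorded at an attended visit stays in that visit's ITT data.
- **PP figures.** PP requires 12 weeks of treatment. A patient who stops ATI-450 early is outside PP whether or not follow-up continues, so for that patient the PP rate reflects the PP definition and the change proposed here would not alter it.
- **ITT figures.** The imputation rules are deferred to the SAP, so the ITT column holds only if missing patients are imputed like those who remain. The proportions do not carry over to time to relapse.

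A reader might infer that withdrawal ends safety observation for the primary endpoint. It does not: Section 7.3 continues AE and SAE reporting to at least 30 days after the last dose, and Section 7.5 follows events to resolution or stabilisation. Some scheduled laboratory and vital-sign assessments can be lost.

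A reader might also infer that both deciding parties do know the efficacy outcome. For the investigator this follows from the PGA role. For the medical monitor it is an inference: Section 5.3.2 gives that person a part in judging abnormal laboratory values, the panel includes hsCRP and SAA, and nothing withholds efficacy data, but no section says that the monitor sees PGA or diary data.

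What the reply does not remove is an unrestricted power to end scheduled follow-up, with the resulting gaps left to imputation or to an earlier visit.

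**Conclusion.** The concern holds as a gap in the wording. Sections 11.2 and 4.4.2 permit outcome-dependent loss of scheduled follow-up in dosed patients, and existing safeguards reduce this without closing it. The documents show that selective withdrawal is possible. They do not show that it is intended or likely, and no such reading is supported.

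In the assumed example, losing 1, 2 or 3 failures shifts an apparent remission rate by about 6, 13 or 21 points. This rests on assumed remission counts, assumed numbers lost and, for ITT, imputation at the rate of those who remain. These shifts are small beside the exact interval for 5 of 10, which is 81.3 − 18.7 = 62.6 points wide. They differ from sampling error in that they run in one direction, towards ATI-450. Because the primary endpoint is safety and the efficacy summaries are descriptive, this is a worthwhile correction and not a fatal flaw.

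**What to change.** 1. **Section 11.2.** State that an important deviation in a dosed patient is not by itself a reason to end study follow-up. Whether ATI-450 continues is decided under Section 4.4.1. The patient is asked to keep the remaining scheduled visits, including Visits 7 and 8, unless consent is withdrawn or attendance would be unsafe. The visits must be named because Section 4.4.1 asks only for the end-of-study assessments.
2. **Section 4.4.2.** Limit both the protocol-violation and the data-integrity grounds in the same way. Changing only one leaves the other route open.
3. **ITT remission analyses.** Count visits after the start of anti-IL-1 or other prohibited therapy during the treatment period as not in remission. They should be neither imputed nor credited to ATI-450. Without this, longer follow-up could record remission regained on the restarted therapy as a success.
4. **Reporting.** List each important deviation with the PGA, hsCRP, SAA and KSS status last recorded before the decision.

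The cost is wording in two sections, one analysis rule and one listing. A few patients off ATI-450 would attend visits already scheduled. A patient given a prohibited drug for an unrelated reason would count as not in remission; any such case judged an important deviation would be visible in the listing. Discretion over the drug under Section 4.4.1 is unchanged; the change separates it from follow-up.
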